## 2 Calcitonin and C-cell abnormalities - evaluation and follow-up

Subjects with a personal or family history of MTC or multiple endocrine neoplasia syndrome type 2 (MEN 2) or with a screening calcitonin  $\geq 50$  ng/L at V2 must be excluded from the trial.

Subjects who are screen failures and have a calcitonin level above the normal range should be referred to their primary care physician and consideration given to referring the subject to a paediatric endocrinologist or thyroid specialist for further evaluation.

A blood sample will be drawn at pre-specified trial visits for measurement of calcitonin. Calcitonin levels will be reviewed monthly by the International Medical Director (IMD) for this project or their surrogate. Calcitonin levels above upper normal limit will be flagged by the central laboratory at the laboratory report, and reported to the investigator, the International Trial Manager (ITM), and IMD. Subject with a calcitonin level post randomisation above the normal limit should be repeated within 4 weeks for confirmation.

If the repeat calcitonin level, or a calcitonin level obtained at a visit is initially  $\geq 20$  ng/L, the subject's abnormal level and clinical data will be forwarded to an external expert. The external expert will report their recommendation to the investigator, the IMD and ITM whether further evaluation is indicated (e.g., referral to a paediatric endocrinologist or thyroid specialist), and whether the subject should discontinue with trial product.

Subjects who have a calcitonin level above the normal range as the last value taken during the trial, should be referred to their primary care physician and consideration given to referring the subject to a paediatric endocrinologist or thyroid specialist for further evaluation.

Liraglutide  
Trial ID: NN8022-4179  
Protocol - Appendix C  
EudraCT No.: 2014-004415-37

~~CONFIDENTIAL~~

Date:	22 December 2017	Novo Nordisk
Version:	3.0	
Status:	Final	
Page:	5 of 5	

**Novo Nordisk**

## Version history

This Statistical Analysis Plan (SAP) for trial NN8022-4179 is based on the final protocol version 5.0 16July2020.

### SAP Version History Summary

SAP Version	Approval Date	Change	Rationale
1		Not Applicable	Original version

# 1 Introduction

## 1.1 Objectives and endpoints

### 1.1.1 Objectives

#### Primary objective

To compare the efficacy of liraglutide versus placebo on weight loss in paediatric subjects with obesity and PWS at 16 weeks and versus no treatment at 52 weeks.

#### Secondary objectives

- To compare the efficacy of liraglutide versus placebo on glycaemic control in children and adolescents with obesity and PWS at 16 weeks and versus no treatment at 52 weeks.
- To estimate the liraglutide steady state exposure in children and adolescents with obesity and PWS after 16 weeks of treatment.
- To compare the safety of liraglutide versus placebo in children and adolescents with obesity and PWS at 16 weeks and versus no treatment at 52 weeks.

### 1.1.2 Endpoints

#### 1.1.2.1 Primary endpoints

There are two co-primary endpoints:

- Change in body mass index (BMI) standard deviation score (SDS) from baseline to 16 weeks
- Change in body mass index (BMI) standard deviation score (SDS) from baseline to 52 weeks

#### 1.1.2.2 Secondary endpoints

##### 1.1.2.2.1 Key supportive secondary efficacy endpoints

- Percent of subjects achieving  $\geq 5\%$  reduction in baseline BMI at weeks 16 and 52
- Percent of subjects achieving  $\geq 10\%$  reduction in baseline BMI at weeks 16 and 52

Change from baseline to 16 and 52 weeks in:

- BMI
- Body weight (kilogram (kg), pounds (lb) and percent (%))
- Hyperphagia score:
  - total score and
  - hyperphagic behaviour, drive and severity score
- Systolic and diastolic blood pressure
- Glucose metabolism: glycosylated haemoglobin (HbA1c), fasting plasma glucose (FPG)

Further details are described in the protocol section 4.2.

Specifications of tables, figures and listings (TFL) and other specifications not included in this SAP will be described in the statistical programming specification (SPS).

Statistical Analysis Plan  
Trial ID: NN8022-4179  
UTN: U1111-1162-7884  
EudraCT No: 2014-004415-37~~CONFIDENTIAL~~Date: 14 December 2020  
Version: 1.0  
Status: Final  
Page: 7 of 36  
Novo Nordisk

## 1.2 Trial design

This is a multi-centre, multi-national randomised, parallel group, placebo-controlled trial with a 16-week double-blind period and a 36-week open-label period. This trial consists of a part A and a part B. Part A of the trial is conducted in adolescents ( $\geq 12$  and  $< 18$  years, Tanner stage 2–5) with obesity and PWS. Part B of the trial is conducted in children ( $\geq 6$  and  $< 12$  years, Tanner stage below 2 (defined as Tanner stage 1 with or without premature adrenarche)) with obesity and PWS. Entry into part A and part B of the trial will be sequential. The randomisation will be stratified according to pubertal status (part A) and by presence/absence of dysglycaemia (Parts A and B). After all subjects in part A have completed the 16-week double-blind period, an independent external Data Monitoring Committee (DMC) will review the PK data and safety data from part A. The DMC will recommend to the Novo Nordisk safety committee whether children in part B should be randomised and exposed to liraglutide/liraglutide placebo. In addition, the tolerability/safety and PK data from trial NN8022-4181 in children with obesity 7-11 years (both inclusive) will be reviewed to allow adjustments in part B.

The maximum duration of treatment of a single subject, from first trial product administration to last trial product administration will be 52 weeks, and the maximum dose will be 3.0 mg/day in part A and for children in part B with a body weight  $\geq 45$  kg. For children in part B with a body weight of  $< 45$  kg the maximum dose will be 2.4 mg/day.

At least 30% of subjects will be from areas with lifestyle and nutrition comparable to that in the European Union (EU).

Further details are described in the protocol section 5.

## 2 Statistical hypotheses

The two co-primary endpoints are:

- Change from baseline in BMI SDS after 16 weeks of treatment
- Change from baseline in BMI SDS after 52 weeks of treatment

The hypotheses of equality between liraglutide and placebo for each of the two endpoints are tested in a hierarchical manner in the order in which the endpoints are presented. The implication is that liraglutide will only be considered statistically significantly better than placebo at 52 weeks if it is considered statistically significantly better with respect to the first primary endpoint.

The primary analysis will include subjects from all strata, i.e. both from part A and part B (provided that the external DMC recommends that part B will be conducted).

BMI SDS will be summarised using descriptive statistics according to the stratification factor for Tanner stage and stratification factor for glycaemic category. In case there are a very low number of subjects within one glycaemic category, the description may be done according to stratification factor for Tanner stage alone.

The analysis of each of the co-primary endpoints will use the same approach and is described below.

The objective is to show that liraglutide is superior to placebo in obtaining weight loss.

Let  $\mu_{\text{liraglutide}}$  and  $\mu_{\text{placebo}}$  denote mean change in BMI SDS for liraglutide and placebo respectively. The null-hypothesis and the alternative hypothesis are:

$H_0: \mu_{\text{liraglutide}} = \mu_{\text{placebo}}$  against the alternative  $H_A: \mu_{\text{liraglutide}} \neq \mu_{\text{placebo}}$

The null-hypothesis will be rejected on a 5% level if the two-sided 95% confidence interval of the treatment difference  $\mu_{\text{liraglutide}} - \mu_{\text{placebo}}$  excludes 0. If the upper limit is below 0 superiority of liraglutide against placebo can be concluded.

Statistical Analysis Plan  
Trial ID: NN8022-4179  
UTN: U1111-1162-7884  
EudraCT No: 2014-004415-37

~~CONFIDENTIAL~~

Date:	14 December 2020	Novo Nordisk
Version:	1.0	
Status:	Final	
Page:	9 of 36	

### 3 Sample size determination

Refer protocol section 17.1.

## 4 Analysis sets

The following analysis sets are defined in accordance with the ICH-E9 guideline.

**Table 4-1 Overview of subject analysis set**

Subject Analysis Set	Description
Full Analysis Set	All randomised subjects who have received at least one dose of trial product and have any post-randomisation data. The statistical evaluation of the FAS will follow the intention-to-treat (ITT) principle and subjects will contribute to the evaluation “as randomised”.
Safety Analysis Set	All subjects exposed to at least one dose of trial product. Subjects in the SAS will contribute to the evaluation “as treated”.

Data from nominal visits (V10x and V19x) will be used prior to imputation of remaining missing data unless otherwise stated.

Before data are locked for statistical analysis, a blind review of all data will take place. Any decision to exclude a subject or single observation from the statistical analysis is the joint responsibility of the trial statistician, the ITM and the medical specialist. Exclusion of data from analyses will be used restrictively and normally no data should be excluded from the FAS. The subjects or observations to be excluded, and the reasons for their exclusion must be documented and signed by those responsible before database lock. The subjects and observations excluded from analysis sets, and the reason for this, will be described in the clinical trial report.

Any observation excluded from the analysis database will be documented before database lock with the reason for exclusion provided.

**Table 4-2 Overview of defined analysis set**

Defined Analysis Data Sets	Description
In-trial	
The time period where the subject is supposed to be in the trial. The in-trial period begins at date of first dose of trial product and ends at the date of:
 
 
• The last direct subject-site contact, which is planned to take place at a follow-up visit
 
• Withdrawal date for subjects who withdraw informed consent
 
• The last subject-investigator/site contact as defined by investigator for subjects who are lost to follow up
 
• Date of death for subjects who die before any of the above
 

On-treatment
	
The time period where subjects are treated with trial product. The on-treatment period begins on the date of first dose of trial product and at the earliest date of:
 
 
• The follow-up visits (subjects with trial product discontinued)
 
• Last day on trial product + 14 days
 
• Last study visit (early withdrawn subjects without FU visit).
 
 
On-treatment period is defined for Liraglutide 3.0 mg as week 0-52 and for Placebo week 0-16.

Double blinded
	
The double blind period is from first dose of trial product to week 16 (0-16).
 
For the events occurring in double blinded period (AE and Hypoglycaemic episode)
 
 
• For liraglutide double blinded period will be from (week 0) to (week 16)
 
• For placebo double blinded period will be from (week 0) to (week 16 + 14 days)
 

Open label
	
The open label period is of duration 36 weeks that is from end of week 16 to week 52.
 
For the events occurring in open label period (AE and Hypoglycaemic episode)
 
 
• For Liraglutide open label period will be from (end of week 16) to (52 weeks + 14 days)
 
• For placebo open label period will be from (end of week 16 +14 days ) to (week 52)
 

## 5 Statistical analyses

### 5.1 General considerations

Results from the statistical analysis will generally be presented by two-sided confidence intervals (CIs) with a confidence level of 95%. Superiority will be claimed if the two-sided p-value is less than 5% and the treatment estimate favours liraglutide. If the upper limit is below 0, superiority of liraglutide against placebo can be concluded.

The full analysis set (FAS) will be used in the analysis of the efficacy endpoints. For the safety endpoints, the safety analysis set (SAS) will be used. The definition of the analysis sets is given in Section [4](#).

The baseline value will be defined as the last measured and available value from V3 (randomisation) and V2 (screening). Laboratory and PK values below the lower limit of quantification (LLOQ) will be set to  $\frac{1}{2}$ LLOQ.

All analysis will be performed for part A , part B and all subject (which includes both part A and B).

### 5.2 Subject disposition

Refer mock TFLs.

### 5.3 Primary endpoints analysis

#### 5.3.1 Primary endpoints

The two co-primary endpoints are:

- Change from baseline in BMI SDS after 16 weeks of treatment
- Change from baseline in BMI SDS after 52 weeks of treatment

The hypothesis mentioned in section [2](#) will be tested using an analysis of covariance (ANCOVA) model using including the factors, covariates and interaction term listed in below table.

**Table 5-1 Factors and covariates for the analysis of the primary endpoints**

Factors and covariates at baseline	Type	Categories
Randomised treatment	Factors	Liraglutide 3.0 mg, Placebo
Sex	Factors	Female, Male
Region	Factors	Asia, Europe, North America, Oceania
Glycaemic category	Factors	Yes, No*
Tanner stage, Glycaemic category	Interaction factor	Not applicable
Tanner stage	Factors	Part A: stage 2 and 3 together, Stage 4 and 5 together Part B: stage 1 with or without premature adrenarche
BMI SDS	Covariate	Not applicable
Age	Covariate	Not applicable

\*Yes: dysglycaemic, No: non-dysglycaemic.

The estimated treatment difference between liraglutide 3.0 mg and placebo will be reported together with the associated two-sided 95% CI and corresponding p-value.

Missing data will in the main analysis be handled by the following multiple imputation (MI) method. A pattern mixture model approach is applied where withdrawn subjects with missing values are assumed to respond as if treated with placebo for the entire trial. Multiple copies (N = 1000) of the full dataset will be generated by imputing missing values based on estimated parameters for the placebo group. These missing data will be handled as mentioned in protocol section 17.3.

**Table 5-2 Taxonomy for subjects based on of week 16 and 52 assessments being available or missing**

Assessment at week 16 and 52	On randomised treatment at week 16 and 52	Type description	Type abbreviation
Available	Yes	Available on randomised treatment: Subjects who did not discontinue randomised treatment prematurely with an assessment at week 16 and 52.	AT
	No	Available drop-outs: Subjects who discontinued randomised treatment prematurely but returned to have an assessment at week 16 and 52; also called retrieved drop-outs.	AD
Missing	Yes	Missing on randomised treatment: Subjects who did not discontinue randomised treatment prematurely without an assessment at week 16 and 52.	MT
	No	Missing drop-outs: Subjects who discontinued randomised treatment prematurely and did not return to have an assessment at week 16 and 52; also called non-retrieved drop-outs.	MD

### 5.3.2 Main analytical approach

#### 5.3.2.1 Handling of missing values at baseline

If an assessment has been made both at screening and randomisation, the value from the randomisation visit will be used as the baseline value. If the value is missing at the randomisation visit and an assessment was available at screening, then the screening value will be used as the baseline value.

#### 5.3.2.2 Handling of missing values at weeks 16 and 52

Missing values at weeks 16 and 52 will be imputed and the relevant endpoints will be analysed from the imputed values. Several approaches for imputation of missing values at weeks 16 and 52 will be applied. First, a description of the primary imputation approach used to address the effectiveness for the primary endpoint is given. This is followed by a description of several sensitivity analyses.

**Primary approach for handling missing values**

The primary approach for multiple imputations of missing values of BMI SDS at week 16 and 52 (type MT+MD [Table 5-2](#)) for both the liraglutide 3.0 mg and placebo group is by sampling all available assessments at respective landmark visits in the placebo group (type AT+AD). This approach is also known as jump to reference and makes the assumptions that subjects instantly after discontinuation lose any effect of randomised treatment beyond what can be expected from placebo treatment as adjunct to diet and exercise. The multiple imputation approach is done in four steps.

**Imputation:** Step 1: 1000 copies of the dataset will be generated.

**Analysis:** Step 2: Impute the missing value from placebo completers by fitting enriched regression model. Model will be fitted with the factors, covariates and interaction term in the same order as mentioned in [Table 5-3](#). The estimated parameters and their variances from this model were used to impute missing values at 16 weeks (or 52 weeks) for subjects in both treatment arms, based on their factor levels and the values of the covariates.

**Analysis:** Step 3: For each of the 1000 complete datasets, the change from baseline in BMI SDS at 16 weeks (or 52 weeks) will be analysed using the main ANCOVA model with factors and covariates and interaction term as mentioned in [Table 5-1](#).

**Pooling:** Step 4: Pool the 1000 estimation results into final result using Rubin's formula.

If N = 1000 copies are insufficient to obtain stable results, a higher number will be used.

The imputation model in step 2 uses placebo subjects from FAS with non-missing BMI SDS at baseline and 16 weeks (or 52 weeks). The imputation model is a linear regression of BMI SDS at 16 weeks (or 52 weeks) on the factors and covariates listed in [Table 5-3](#) (except randomised treatment arm) with interaction term included in the model. The order of the factors and covariates has been retained as mentioned in [Table 5-3](#) while fitting imputation model. The estimated posterior distribution for the parameters (regression coefficients and variances) in the imputation model is then used to impute missing 16 weeks (or 52 weeks) BMI SDS values for both randomised treatment arms.

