**CONFIDENTIAL**

Date:	16 July 2020	Novo Nordisk
Version:	5.0	
Status:	Final	
Page:	93 of 125	

values are assumed to respond as if treated with placebo for the entire trial. Multiple copies (N = 1000) of the full dataset will be generated by imputing missing values based on estimated parameters for the placebo group. This will be done as follows.

- In the first step, N = 1000 copies of the dataset will be generated.
- In the second step, an enriched ANCOVA model with sex, region, stratification factor for Tanner stage, baseline glycaemic category and interaction between baseline glycaemic category and stratification factor for Tanner stage as fixed effects and baseline BMI SDS, as covariate is fitted to the change from baseline in BMI SDS at 16 weeks (or 52 weeks) for the completers in the placebo group only.
- For each of the N copies of the dataset, the estimated parameters and their variances from this model are used to impute missing values at 16 weeks (or 52 weeks) for subjects in both treatment arms, based on their factor levels and the values of the covariates.
- For each of the N complete datasets, the change from baseline in BMI SDS at 16 weeks (or 52 weeks) is analysed using the main ANCOVA model with treatment, sex, region, baseline glycaemic category, stratification factor for Tanner stage and interaction between baseline glycaemic category and stratification factor for Tanner stage as fixed effects, and baseline BMI SDS and baseline age as covariates.
- The estimates and SDs for the N data sets are pooled to one estimate  $m_{MI}$  and associated  $SD_{MI}$  using Rubin's formula:

$$m_{MI} = \frac{1}{100} \sum_{i=1}^{100} m_i, \quad SD_{MI} = \sqrt{\frac{1}{100} \sum_{i=1}^{100} SD_i^2 + \left(1 + \frac{1}{100}\right) \left(\frac{1}{100 - 1}\right) \sum_{i=1}^{100} (m_i - m_{MI})^2},$$

where  $m_i$  and  $SD_i$  are the estimated means and standard deviations for the N copies of the dataset. From  $m_{MI}$  and  $SD_{MI}$ , the 95% CI for the treatment difference and the associated p-value are calculated.

If N = 1000 copies are insufficient to obtain stable results, a higher number will be used.

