**Novo Nordisk**

estimable: region, sex, baseline BMI SDS, Tanner stage, baseline glycaemic category and interaction between baseline glycaemic category and stratification factor for Tanner stage.

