**Table 5-3 Factors and Covariate for imputation model**

Factors and covariates at baseline	Type	Categories	Order
Sex	Factors	Female, Male	1
Region	Factors	Asia, Europe, North America, Oceania	2
Tanner stage	Factors	Part A: Stage 2 and 3 together, Stage 4 and 5 together Part B: Stage 1 with or without premature adrenarache	3
Glycaemic category	Factors	Yes, No	4
Glycaemic category, Tanner stage	Interaction factor	Not applicable	5
BMI SDS	Covariate	Not applicable	6

The multiple imputations will be generated using Novo Nordisk trial number 80224179 as seed number.

If the imputation ANCOVA model cannot be estimated due to too few placebo subjects with available data, explanatory variables will be removed in the following order until the model is estimable: region, sex, baseline BMI SDS, Tanner stage, baseline glycaemic category and interaction between baseline glycaemic category and stratification factor for Tanner stage.

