## 6.2 Appendix 2: Changes to protocol-planned analyses

In this SAP the following changes is been made to the statistical consideration in the protocol are as elaborated below for:

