### 6.2.2 Supportive secondary efficacy endpoints

- Additional analysis for changes from baseline at 16 and 52 weeks
  - BMI SDS (%)
  - BMI (%)

It will be analysed with the same type of ANCOVA with MI as used for the main analysis of the primary endpoint, with the corresponding baseline covariate.

- During the blinded review of data it has been observed that there were only few subjects achieving  $\geq 10\%$  reduction in baseline BMI at week 16 or at week 52 (as mentioned in section [5.4.1](#)). Therefore the statistical analysis (J2R-MI Logistic Regression) will not be performed for this endpoint and will be summarised descriptively.
- For the analysis of categorical endpoints , the protocol mentions to include treatment, sex, region, baseline glycaemic category, stratification factor for Tanner stage and interaction between baseline glycaemic category and stratification factor for Tanner stage as fixed effects, and baseline BMI/BMI SDS (wherever applicable) and baseline age as covariates. During the blinded review of data for the categorical endpoints it has been observed that due to the small number of subjects in the trial the model cannot be estimated. To avoid the risk of over fitting and to make the model estimable the following explanatory variables will be removed from the analysis model.: sex, region ,interaction between baseline glycaemic category and stratification factor for Tanner stage.
- During the blinded review of data it has been observed that no subject reported an amylase measurement above 3UNR and only one subject reported a lipase measurement above 3UNR. Due to the few number of subjects having a measurement above 3UNR,for these parameters at any time during treatment, the statistical analysis (Logistic Regression) will not be performed.

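### The SAP imputes the BMI SDS level where the protocol imputes the change from baseline; the two diverge, at a cost in precision, if the fallback drops baseline BMI SDS

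*SAP*

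**What the plan says.** Both documents impute missing BMI SDS from a regression fitted to placebo subjects with available data, then analyse the change from baseline by ANCOVA. They name different responses for that regression.

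- Protocol 17.3, second step: the model "is fitted to the change from baseline in BMI SDS at 16 weeks (or 52 weeks) for the completers in the placebo group only".
- SAP 5.3.2.2, primary approach: "The imputation model is a linear regression of BMI SDS at 16 weeks (or 52 weeks", on the terms in SAP Table 5-3.
- SAP 5.3.1, under Table 5-1: "These missing data will be handled as mentioned in protocol section 17.3". The SAP therefore points to the protocol's method and also writes out a different one.
- SAP Appendix 2 (6.2) sets out that "the following changes is been made to the statistical consideration in the protocol". Its entries for the primary endpoints (6.2.1) cover COVID-19 measurements and the use of V10x and V19x data in the sensitivity analyses. They do not mention the imputed response.

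The fallback for too few placebo subjects is the same in both. The SAP wording under Table 5-3 is that terms are "removed in the following order until the model is estimable: region, sex, baseline BMI SDS, Tanner stage, baseline glycaemic category and interaction"; Protocol 17.3 has the same list. Baseline BMI SDS goes third and the interaction last. Neither document defines when the model counts as not estimable, how the factors are coded, or whether the interaction must go when one of its main effects goes.

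**The concern.** This model feeds the main analysis of both co-primary endpoints. If the response is the level and baseline BMI SDS is not in the model, a child's imputed value takes no account of where that child started. Subtracting the child's own baseline to obtain the change then adds the full between-child spread of BMI SDS to every imputed change. With about 6 of 57 subjects missing at week 16, that noise could swamp the treatment comparison. The protocol may be meant to govern, but the explicit sentence in SAP 5.3.2.2 is the one a programmer would follow.

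**Working it through.** **The plan's own figure.** Protocol 17.1 gives a difference of -0.23, SD 0.25, 10% withdrawal and 2:1 allocation. Corrected difference: 0.9 × 0.23 = 0.207. Corrected SD: √(0.25² + (2/3)(0.1)(0.9)(0.23²)) = 0.256. A two-sided 5% t-test with 38 and 19 subjects has 80.6% power, so the stated 57 is reproduced.

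**When the two responses agree.** Write level = change + baseline. If baseline is a regressor, switching from change to level adds exactly 1 to its coefficient and leaves every other coefficient, the residuals and the residual variance unchanged. With the same random draws, imputed level minus baseline equals imputed change; numerically the difference is below 2 × 10⁻¹⁴.

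**When they part.** Without baseline in the model, and with change unrelated to baseline, an imputed level has variance SD_base² + 0.25². Subtracting the child's own baseline adds SD_base² again, so the imputed change has SD √(2·SD_base² + 0.25²). The documents give no SD_base. For assumed values of 0.5, 0.9 and 1.3 this is 0.75, 1.30 and 1.86, instead of 0.25.

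**Can the fallback reach baseline?** Coefficients in SAP Table 5-3: intercept 1 + sex 1 + region 3 + Tanner 2 + glycaemia 1 + interaction 2 + baseline 1 = 11. Placebo subjects available: 19 × 0.9 ≈ 17 at week 16 and 19 × 0.8 ≈ 15 at week 52. Numbers alone would not push the list to its third step, because removing region and sex leaves 7 coefficients. An empty placebo cell among the six Tanner-by-glycaemia cells could. With class-factor terms and one empty cell:

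| Model | Rank needed / available |
|---|---|
| Full | 11 / 10 |
| minus region | 8 / 7 |
| minus sex | 7 / 6 |
| minus baseline BMI SDS | 6 / 5 |
| minus Tanner | 6 / 5 |
| minus glycaemia | 6 / 5 |
| minus interaction (intercept only) | 1 / 1 |
| Alternative: region, sex and interaction out, rest kept | 5 / 5 |

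Removing region, sex or baseline cannot cure an empty cell under any coding. Later steps depend on coding. With sum-to-zero product columns, all six single-empty-cell cases become estimable when Tanner goes. With reference coding, three of six do at that step and four of six once glycaemia goes. In every case baseline has already been lost.

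**Size at week 16, conditional on baseline having been dropped, 10% missing.** Missing liraglutide subjects respond as placebo; 50 imputations, Rubin pooling.

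- Simplified simulation (57 subjects, ANCOVA on treatment and baseline), baseline SD 0.5 / 0.75 / 1.0: mean SE 0.111 / 0.142 / 0.176 with level against 0.077 with change; power 46 / 23 / 14% against 78%. The mean estimate barely moves: -0.204 to -0.207 against -0.211.
- A further simplified run, baseline SD 0.5 / 0.9 / 1.3: power about 40 / 20 / 8% against 78-79%.
- Fuller simulation (stratified 2:1 blocks of 3, fallback run step by step with class-factor terms; dysglycaemia 10-40%, three region mixes and Tanner 4-5 in 65% of Part A, all assumed), baseline SD 0.5 / 0.9 / 1.3: power 33-35 / 9-15 / 5-7% against 66-71%; median SE 0.12-0.25 against 0.082-0.083. At 5% missing (one reference mix): 51-57 / 32 / 14-16% against 77-83%.

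SE ratios: 0.111/0.077 = 1.4 at the low end and 0.25/0.083 = 3.0 at the high end.

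**How often.** In the fuller simulation at 10% missing, baseline is dropped in 9-25% of trials if the trigger is that a subject needing imputation cannot be predicted. It is dropped in 15-70% if any non-estimable coefficient is enough. At baseline SD 0.9 the conditional loss is about 55 points, so the overall loss under the narrower trigger is roughly 0.09 × 55 ≈ 5 to 0.25 × 55 ≈ 14 points.

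**Null case.** With a true difference of 0 and baseline dropped, rejection in favour of liraglutide is 0.2% with level and 1.1-1.2% with change, against a nominal 2.5%.

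**The case against.** The best defence is that the mismatch may never bite. SAP 5.3.1 defers to Protocol 17.3, so the protocol's response may be intended. The model has fewer coefficients than placebo subjects, software using a generalised inverse need not stop at an empty cell, and predictions for populated cells are unaffected. V10x and V19x data are used before imputation, which cuts missingness. All of this stands, and it is why the figures above are conditional. It does not remove the contradiction: two responses are written and the trigger is undefined.

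A reader might infer from SAP 6.2.2 that this model has already failed, since for the categorical endpoints "it has been observed that due to the small number of subjects in the trial the model cannot be estimated". That goes too far. Those are logistic models on all subjects, so the remark is a warning about the same factor set and does not show that the placebo linear regression fails.

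A reader might also infer that the fallback can only end at an intercept-only model. That holds if the interaction is a class term spanning all six cells. The documents do not state the coding, and other codings stop earlier.

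Nor is the shared order a defect with a demonstrated cost of its own. The two documents agree on it, and with change as the response it costs little.

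**Conclusion.** The point holds as an undeclared contradiction between the SAP and the protocol in the primary imputation model. It is harmless while baseline BMI SDS is in the model and costly if the fallback removes it. In that event, with 10% missing and the SAP programmed as written, the SE is roughly 1.4 to 3 times larger. Conditional power at week 16 is then about 33-46% at baseline SD 0.5, 9-20% at 0.9 and 5-8% at 1.3, against about 66-79% with the protocol's response. The overall loss at baseline SD 0.9 is roughly 5 to 14 points under the narrower trigger, and more under the wider one.

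The identity and rank results are exact for the codings named. The sizes rest on assumed baseline SD, dysglycaemia prevalence, Tanner split and region mix, and are illustrative. No week-52 power is claimed.

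A reader might infer a biased or falsely positive primary result. The calculations do not support that: the estimate hardly moves and rejection under the null falls below nominal. The LOCF, BOCF, completer and MMRM analyses do not use this model.

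**What to change.** State in SAP 5.3.2.2 that the imputation response is the change from baseline in BMI SDS, as in Protocol 17.3. In the same place define when the model cannot be estimated: for example, when a subject needing imputation cannot be predicted from the placebo data, or when no residual degrees of freedom remain. This costs SAP wording and one model statement before the unblinded analysis, and needs no extra data.

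Optional: remove the interaction after region and sex, and keep baseline BMI SDS to the end. The SAP took out the same three terms for the categorical endpoints, for this reason: "To avoid the risk of over fitting and to make the model estimable the following explanatory variables will be removed from the analysis model". Because the order also stands in Protocol 17.3, this would have to be declared in Appendix 2 as a change from the protocol. No power gain is claimed for it on the change scale. In the fuller simulation it costs 0-3 points overall, and 3-7 points when the fallback is triggered, if the retained covariates do not predict response. In return, the imputation keeps baseline and the stratification factors.
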